3.7 ATRA Dose and Duration in Non-APL AML

There are no clinical studies comparing doses of ATRA in the treatment of APL. The standard dose is 45 mg/m² per day in divided doses, though some reports suggest that a reduced dose of 25 mg/m² is equally effective (Tallman and Altman 2009). Daily dosing of ATRA is typically continued until complete remission (CR) by clinical measures has been achieved, as long as the patient is tolerating treatment well. Patients who have received ATRA for at least two weeks but were discontinued because of toxicity even eventually achieved CR. After the induction of CR, APL patients receive intermittent ATRA for up to 2 years to achieve a molecular remission.

Though very low doses of ATRA in combination with IMG-7289 were needed to induce differentiation in cultured AML cells, higher exposure to ATRA than that needed for differentiation may be required to induce AML cell death (apoptosis) and potentially reduce the leukaemic stem cell pool. Hence, in combination with IMG-7289, the proposed dose of ATRA is 45 mg/m² per day divided into two doses.

The objective of this phase of the study is to expose leukaemic cells to a combination of both IMG-7289 and ATRA. Non-clinical models had suggested the half-life of IMG-7289 was less than 24 hours. The PK parameters now available for the first four dose-finding sub-cohorts indicate a drug half-life of 4-5 days. Thus, what was originally defined as the 7 day “rest” period is one during which patients are still exposed to IMG-7289 at or above the IC₅₀ of the drug. This degree of exposure has, however, been demonstrated to be well tolerated. Thus, to match more closely the exposure of ATRA to IMG-7289, ATRA will be given at the planned dose of 45 mg/m², but for 21 days, followed by a rest period of 7 days. This dosing schedule of ATRA is regarded as safe as it affords less exposure than standard recommended treatment regimens of ATRA for acute promyelocytic leukaemia in which 45-60 days of daily ATRA at 45 mg/m² would be most common.

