6.8 Treatment Failure

Patients who either fail to demonstrate stable disease, demonstrate progressive disease after achieving partial remission or stable disease, or relapse after achieving CR, CRi or PR (see **Table 14** and **Table 15**) are the equivalent of treatment failures, and will discontinue study drug and enter the follow-up period.

CCI

CCI

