8.2.1 IMG-7289 Toxicity Definitions

Haematologic Toxicity: Haematologic values outside of the normal reference range are inherent features of AML and MDS, and are expected effects of many therapeutic attempts to manage these diseases. These effects will not be considered DLTs.

Both genetic knockdown (KD) of LSD1 mRNA and pharmacologic inhibition of LSD1 show that the loss of LSD1 activity arrests the production of mature red cells, platelets and granulocytes while over-producing monocytes (Sprussel *et al.*, 2012; Kerenyi *et al.*, 2013). Production of cells of lymphoid lineage, B and T cells is unimpaired indicating that LSD1 has very cell-specific functions and its inhibition also has very specific effects. LSD1 inhibition in AML cells causes the induction of monocytic differentiation markers, as well as a reduction of self-renewal potential of leukaemic cells, eventually resulting in apoptosis of treated cells. Thus, the anaemia, thrombocytopenia, neutropenia and monocytosis attending LSD1 inhibition, as observed in animals treated with IMG-7289, reflect primary pharmacodynamic effects. The kinetics of anaemia, thrombocytopenia, and neutropenia following complete LSD1 inhibition are a function of the lifespan of the individually affected cell types. Over the course of LSD1 inhibition, platelet and neutrophil counts are the most affected, reflecting their short mean lifespans of approximately seven and twelve days, respectively. Recovery of peripheral counts is reversible, rapid, and temporarily overshoots baseline values. At lower doses, the effects on haematopoiesis are much less pronounced suggesting that a modicum of residual LSD1 activity is sufficient to support some blood cell formation. Thus, both the duration of LSD1 inhibition as well as the degree of inhibition are critical to the pharmacodynamic effects on myeloid lineages.

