The intended dosing plan for high risk AML/MDS patients is predicated on the supposition that LSD1 must be maximally inhibited to achieve the greatest therapeutic benefit. The concentrations of LSD1 inhibitors such as IMG-7289 (free base) used to achieve maximal effects on growth, differentiation and apoptosis *in vitro* with primary patient-derived AML cells as well as AML cell lines are similar to concentrations that *in vivo* inhibit red cell, platelet and granulocyte production. It is therefore expected that high risk AML/MDS patients will require treatment at doses sufficient to induce profound thrombocytopenia and neutropenia. These drug-induced but reversible cytopenias can be managed clinically as needed with platelet and red cell transfusions as well as broad-spectrum antibiotics in the case of febrile neutropenia, as are already standard practices in the routine management of AML/MDS patients receiving intensive SOC chemotherapy.

The effects of IMG-7289 on normal myeloid haematopoiesis observed in non-clinical studies are expected in humans; these are pharmacodynamic effects of LSD1 inhibition by IMG-7289, thus are not regarded as adverse. These events, with the exceptions noted below, will not be considered DLTs.

Dose Limiting Toxicity (DLT): DLT is defined as any one of the following AEs that occurs during the first cycle of therapy and is considered by the Investigator to be possibly, probably or definitely related to IMG-7289.

- A clinically significant bleeding event;
- Any Grade 4 or 5 non-haematologic adverse event;

- Any Grade 3 non-haematologic adverse event with failure to recover to Grade 1 within 7 days of drug cessation, with the following exceptions:
 - ≥ Grade 3 nausea, vomiting or diarrhoea that responds to standard medical care
 - ≥ Grade 3 aesthenia lasting less than 14 days
- Any Grade 3 electrolyte abnormality unrelated to the underlying malignancy and persisting greater than 24 hours.

Patients who experience a dose limiting toxicity (DLT) will have their dose adjusted downward if the Medical Monitor and Principal Investigator deem it safe for the patient to continue on IMG-7289. To ensure a minimum of 3 Cycle 1 completers, and contingent on the number of prior DLTs within the sub-cohort/cohort, such patients may be replaced.

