*All criteria need to be fulfilled; marrow evaluation should be based on a count of 200 nucleated cells in an aspirate with spicules; if ambiguous, consider repeat exam after 5 to 7 days; flow cytometric evaluation may help to distinguish between persistent leukaemia and regenerating normal marrow; a marrow biopsy should be performed in cases of dry tap, or if no spicules are obtained; no minimum duration of response required.
¶In cases with low blast percentages (5-10%), a repeat marrow should be performed to confirm relapse. Appearance of new dysplastic changes should be closely monitored for emerging relapse. In a patient who has been recently treated, dysplasia or a transient increase in blasts may reflect a chemotherapy effect and recovery of haematopoiesis. Cytogenetics should be tested to distinguish true relapse from therapy-related MDS/AML.

Table 15: Response Criteria for MDS

Category	Response Criteria (responses must last at least 4 weeks)
Complete remission	Bone marrow: ≤ 5% myeloblasts with normal maturation of all cell lines* Persistent dysplasia will be noted*† Peripheral blood‡ Hgb ≥ 11 g/dL Platelets ≥ 100 x 10 ⁹ /L Neutrophils ≥ 1.0 x 10 ⁹ /L† Blasts 0%
Partial remission	All CR criteria if abnormal before treatment except: Bone marrow blasts decreased by ≥ 50% over pretreatment but still > 5% Cellularity and morphology not relevant
Marrow CR†	Bone marrow: ≤ 5% myeloblasts and decrease by ≥ 50% over pretreatment† Peripheral blood: if HI responses, they will be noted in addition to marrow CR†
Stable disease	Failure to achieve at least PR, but no evidence of progression for > 8 wks
Failure	Death during treatment or disease progression characterized by worsening of cytopenias, increase in percentage of bone marrow blasts, or progression to a more advanced MDS FAB subtype than pretreatment
Relapse after CR or PR	At least 1 of the following: Return to pretreatment bone marrow blast percentage Decrement of ≥ 50% from maximum remission/response levels in granulocytes or platelets Reduction in Hgb concentration by ≥ 1.5 g/dL or transfusion dependence
Cytogenetic response	Complete: Disappearance of the chromosomal abnormality without appearance of new ones Partial: At least 50% reduction of the chromosomal abnormality

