Disease progression	For patients with: Less than 5% blasts: ≥ 50% increase in blasts to > 5% blasts 5%-10% blasts: ≥ 50% increase to > 10% blasts 10%-20% blasts: ≥ 50% increase to > 20% blasts 20%-30% blasts: ≥ 50% increase to > 30% blasts Any of the following: At least 50% decrement from maximum remission/response in granulocytes or platelets Reduction in Hgb by ≥ 2 g/dL Transfusion dependence

Category	Response Criteria (responses must last at least 4 weeks)
Survival	Endpoints: Overall: death from any cause Event free: failure or death from any cause PFS: disease progression or death from MDS DFS: time to relapse Cause-specific death: death related to MDS

To convert haemoglobin from grams per deciliter to grams per liter, multiply grams per deciliter by 10.

MDS indicates myelodysplastic syndromes; Hgb, haemoglobin; CR, complete remission; HI, haematologic improvement; PR, partial remission; FAB, French-American-British; AML, acute myeloid leukaemia; PFS, progression-free survival; DFS, disease-free survival.

*Dysplastic changes should consider the normal range of dysplastic changes (modification).

†Modification to IWG response criteria.

#Transient cytopenias during repeated chemotherapy courses should not be considered as interrupting durability of response, as long as they recover to the improved counts of the previous course.

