Additionally, the Kaplan-Meier method will be used to analyze event-free survival (EFS) and overall survival (OS); Summaries will present the number (%) of subjects with events, the number (%) of subjects without events (censored), the median (95% CI) survival, and the probability of 6-month survival. OS is defined as the time interval between treatment start date and death date, and OS will be censored at the last date known alive. EFS is defined as the time interval between the date of treatment start and date of resistance, relapse, progression, or death. For subjects that do not have an event, EFS will be censored at the date of last tumor assessment prior to any concurrent cancer chemotherapy and transfusion.

IX. Safety Analysis

The safety and tolerability of IMG-7289 with and without ATRA will be assessed by the analysis of adverse events (AEs), as well as changes in physical examinations, vital signs, laboratory values and ECGs as detailed below, using the Safety Population.

A. Adverse Events

The AEs reported on the eCRFs will be coded using the latest version of MedDRA available to the sponsor at the time of study initiation (up-versioning will not occur), associating lower-level terms with preferred terms and system organ classes (SOC) by the primary hierarchy. The tables will display counts and percentages of subjects who reported at least one AE in each system organ class represented in the AE data. Within each system organ class, the tables will display the counts and percentages of subjects reporting at least one AE, as designated by the preferred terms.

In any given category (e.g., SOC or preferred term) a patient will be counted only once. If a patient has the same AE on multiple occasions, only the highest toxicity grade will be used. Similarly, only the most related event will be used. Percentages will be based on the number of patients in the subgroup of patients being tabulated and not the number of events. Summaries that are displayed by system organ class and preferred terms will be ordered by descending order of incidence of system organ class and preferred term within each system organ class.

Treatment-emergent adverse events will be summarized. Only those events with an onset date on or after the date on which IMG-7289 was first dispensed, and within 28 days of last IMG-7289 treatment are to be recorded on the AE eCRF; therefore, all reported AEs are expected to be treatment-emergent. However, if eCRF completion

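### Table 15 does not separate expected, reversible drug-induced cytopenia from MDS progression or failure, so the same on-target effect can be read as treatment failure, an EFS event and loss of stable disease

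*Protocol*

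**What the plan says.** **Expected drug effect.** Protocol 8.2.1 describes anaemia, thrombocytopenia and neutropenia as primary pharmacodynamic effects and not as adverse. It continues: "It is therefore expected that high risk AML/MDS patients will require treatment at doses sufficient to induce profound thrombocytopenia and neutropenia". It adds: "These drug-induced but reversible cytopenias can be managed clinically as needed with platelet and red cell transfusions". It also says that the effects are much weaker at lower doses. Section 3.7 reports a half-life of 4-5 days and says that the 7-day rest period "is one during which patients are still exposed to IMG-7289 at or above" the IC50.

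**MDS criteria (Protocol 16.2, Table 15).** The disease progression row gives blast rises by starting category, then a list of which any may apply: "At least 50% decrement from maximum remission/response in granulocytes or platelets", a haemoglobin fall of at least 2 g/dL, or transfusion dependence. The failure row names death during treatment or "disease progression characterized by worsening of cytopenias", a rise in marrow blasts, or a more advanced FAB subtype. Stable disease is less than PR with no evidence of progression for more than 8 weeks. One footnote says that transient cytopenias during repeated chemotherapy courses do not break durability of response if counts recover to the improved level.

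**Consequences.** Under Protocol 6.8, patients who do not reach stable disease, progress after PR or stable disease, or relapse "are the equivalent of treatment failures, and will discontinue study drug and enter the follow-up period". SAP VIII.A runs EFS to the "date of resistance, relapse, progression, or death". Without an event, EFS is censored at the last tumour assessment before concurrent chemotherapy and transfusion. The same SAP section counts stable disease as objective response. It takes the investigator's response call at each post-baseline marrow.

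**Text pointing the other way.** Sections 5.1, 7.2.2.3 and 8.1 let the DSMC lengthen the rest period when haematopoiesis has not recovered. In additional cycles, rest may reach 56 days, and a very hypocellular marrow attributed to myelosuppression is one of the listed reasons. Section 5.1 also allows transfusions for expected cytopenias.

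**The concern.** One part of the protocol tells the site that falling counts and transfusions are the drug working. Another lists falling haemoglobin, transfusion dependence and worsening cytopenias as ways for an MDS patient to progress or fail. Nothing says which reading governs when the marrow blasts have not changed.

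The stakes are interpretive. SAP VIII.A uses these responses for a primary objective, the adequacy of dose and duration. If sites differ in how they read an expected cytopenia, EFS and ORR in MDS patients will partly measure that difference. AML progression in Table 14 is based on blasts, so the problem is specific to MDS.

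**Working it through.** The plan has no figure to reproduce here. The check is a side-by-side reading, then a plausibility calculation.

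**1. What each count-based MDS criterion needs**

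| Criterion (Table 15) | Reference level stated | Applies to a patient who never responded? | Drug effect excluded? |
|---|---|---|---|
| Granulocytes or platelets down at least 50% | Maximum remission/response | No defined reference | No |
| Haemoglobin down at least 2 g/dL | None | Yes, as written | No |
| Transfusion dependence | None | Yes, even if already present at entry | No |
| Worsening of cytopenias (failure row) | None in that phrase | Yes, as written | No |

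The footnote does not close the gap. It concerns durability of a response already reached, refers to chemotherapy although the synopsis and 5.1 describe the agent as non-cytotoxic, and requires recovery, which continued exposure during the rest week may delay.

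**2. Could platelets and neutrophils fall by half?** Section 8.2.1 says that these counts are the most affected, "reflecting their short mean lifespans of approximately seven and twelve days, respectively". Take L = 7 days for platelets and 12 for neutrophils. With a fraction f of production stopped throughout, the exponential fall at day t is f × (1 − exp(−t/L)).

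- f = 1: a 50% fall takes L × ln 2 = 4.9 and 8.3 days, or L/2 = 3.5 and 6.0 days if the decline is linear.
- f = 1 at day 14: 86.5% and 68.9%; at day 28: 98.2% and 90.3%.
- f = 0.75 at day 14: 64.8% and 51.6%; at day 28: 73.6% and 67.7%.
- f = 0.5 at day 14: 43.2% and 34.4%; at day 28: 49.1% and 45.2%. The limit is f itself, so 50% is never passed.

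The f = 1 figures are an upper bound. They also measure a fall from the starting count, whereas the Table 15 criterion measures from maximum response. Day 14 is not a response time point in the Cohort 1 schedule for Cycles 2-4 (16.1.3), which places marrows on Day 14 of Cycles 2 and 4, about study days 28 and 56. After a 7-day rest, 0.5^(7/4) = 30% to 0.5^(7/5) = 38% of the drug remains.

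**3. Could haemoglobin fall by 2 g/dL?** Assume a red-cell lifespan of 100-120 days, a starting haemoglobin of 8-10 g/dL (neither is in the documents) and full arrest. The fall, by exponential or linear decline, is 0.9-1.4 g/dL at day 14, 1.7-2.8 at day 28 and 3.0-5.6 at day 56. The criterion can therefore be reached around the Cycle 2 marrow, again as an upper bound.

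**4. Where a call leads**

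- Initial treatment lasts 4 × (7 + 7) = 56 days in Cohort 1, 2 × (14 + 7) = 42 in Cohorts 3/3χ and 1 × (21 + 7) = 28 in Cohorts 4/4χ. Stable disease needs more than 56 days, so it cannot be shown within the initial cycles. Until then, a patient without a response reaches 6.8 through not showing stable disease.
- EFS: the SAP counts progression, and Table 15's own event-free definition counts failure. Cytopenia can feed either. A transfused patient with the same counts but no progression call, and no other event, is censored at the last assessment before transfusion.
- ORR: stable disease counts as response, so one call can turn a responder into a non-responder. With three patients that is 1/3 = 33 points. This is the weight of any one patient, not a probability.

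**The case against.** The strongest reply is that the documents do not force this outcome, and much of that stands. The investigator determines response at marrow visits; the SAP does not derive it from counts. The failure row speaks of disease progression shown by cytopenia, so an investigator may decline to call it when the drug explains the fall. Table 15 does not say whether its count-based list is an alternative to the blast criteria or an addition to them. Count-based progression also belongs to the IWG criteria that the protocol adopts for MDS.

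Three stronger readings are tempting, and the documents do not support them:

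- A reader might infer that an MDS patient showing the intended effect must stop drug and is automatically an EFS event. The investigator's role and the extended-rest text show unreconciled instructions, not a single dictated result.
- A reader might infer that nearly every MDS patient crosses the 50% threshold in Cycle 1. That criterion has no reference in a patient who never responded, and the short times assume full arrest and a fall from baseline.
- A reader might infer a bias in the DSMC's choice of the pharmacodynamic dose. Its listed indicators (synopsis and 8.1) are counts, blasts, immunophenotype, allele frequency, cytokines, PSA and PK. The list is open-ended, but it names neither EFS nor Table 15 categories.

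Discretion does not remove the problem. Without a stated rule, patients with the same counts can be recorded as events, censored, or counted as stable disease.

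**Conclusion.** The point holds as an unresolved conflict. The haemoglobin, transfusion-dependence and worsening-cytopenia criteria carry no attribution wording, and transfusion dependence has no baseline. An expected drug effect in an MDS patient can therefore be recorded as progression or failure, with consequences for discontinuation, EFS and ORR. The 50% granulocyte/platelet criterion adds to this mainly in patients who have responded.

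The frequency cannot be estimated: the documents give neither the number of MDS patients nor the depth of inhibition. The count and haemoglobin falls show only that the thresholds are within reach under strong inhibition. The haemoglobin result also rests on an assumed red-cell lifespan and starting level. EFS is planned only if applicable (Protocol 12.7) and the study is not randomised, so the harm is to what EFS and ORR can show in MDS patients. It is not to a formal test.

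**What to change.** In SAP VIII.A:

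- Keep the Table 15 criteria for the main analysis. Counting only blast-based progression there would depart from the adopted criteria and tilt EFS towards the drug.
- Flag and tabulate separately MDS progression or failure called on cytopenia, haemoglobin or transfusion alone, with no marrow-blast or FAB change.
- Add a sensitivity analysis of EFS, and of stable disease and ORR, that does not count those calls.
- For analysis, judge transfusion dependence against the baseline transfusion history already collected (16.1.1 and SAP X.D, a 15-day look-back).
- State the reference level for each count-based criterion, and whether the count list is an alternative or an addition to the blast criteria.

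Across both documents, reconcile Table 15, 6.8, 8.2.1, the extended-rest text in 5.1, 7.2.2.3 and 8.1, and the SAP rules for EFS events and transfusion censoring, so that sites and analysts have one reading. Which clinical rule applies is for the sponsor and investigators; none is proposed here.

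The cost is SAP wording, one table row, one sensitivity analysis and clarifying protocol text. SAP I.B allows changes until database lock. The sensitivity analysis will date some true cytopenia-led progressions later, and the separate row will show them.

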The primary objective, the adequacy of IMG-7289 dose and duration with and without ATRA in producing a pharmacodynamic effect, will be determined using serial blood and bone marrow sampling throughout the course of treatment with responses documented according to revised/modified International Working Group (IWG) Response Criteria – [Cheson *et al.* 2003](#) for AML and [Cheson *et al.* 2006](#) for MDS as described in Protocol Section 16.2. Response is to be assessed each time a bone marrow aspirate or biopsy is performed, with the exception of baseline. All available response data will be listed. The visit overall response per patient, as determined by the Investigator, and recorded on the eCRF, will be listed and summarized for each cohort, using the Efficacy Population.

The best response of each AML patient will be programmatically selected based on the following order: Complete Remission (CR), CR w/Incomplete Recovery (CRi), Morphologic Leukaemia-Free State (MLFS), Partial Remission (PR), Cytogenetic CR (CRc), Molecular CR (CRm), Stable Disease (SD), Resistant Disease (RD), Relapse (Rel), Progressive Disease (PD), Death from Indeterminate Cause (DInd), Death in Aplasia (DiA), and Not Evaluable. The best response of each MDS patient will be programmatically selected based on the following order: Complete Remission (CR), Partial Remission (PR), Marrow CR (CRm), Cytogenetic Response (CyR), Stable Disease (SD), Relapse After CR or PR (Rel), Disease Progression (DP), Failure: Disease Progression (FDP), Survival (Sur), Failure: Death During Treatment (FDDT), and Not Evaluable.

Objective response in AML includes Complete remission (CR), CR with incomplete recovery (CRi), Morphologic leukemia-free state, Partial remission (PR), Cytogenetic CR (CRc), and Molecular CR (CRm) and Stable Disease (SD); while objective response in MDS includes Complete remission (CR), Partial remission (PR), Marrow CR, or Cytogenetic response (CyR) and Stable Disease (SD). Objective response rate (ORR) is the proportion of responders with AML or MDS. ORR and its Fisher exact 95% confidence interval will be presented.

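### The SAP ranks an undefined Survival category above death during treatment in the MDS best-response order, so a treatment death could be labelled Survival

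*Protocol*

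**What the plan says.** Protocol section 16.2, Table 15, sets out the MDS response criteria. Most rows give a condition on marrow, blood counts, blasts or cytogenetics. The Survival row does not. It reads "Endpoints: Overall: death from any cause Event free: failure or death from any cause", goes on to define PFS and DFS, and closes with "Cause-specific death: death related to MDS". The Failure row of the same table includes death: "Death during treatment or disease progression characterized by worsening of cytopenias".

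SAP VIII.A takes the response at each marrow assessment from the investigator's eCRF entry and then derives one value per patient: "The best response of each MDS patient will be programmatically selected based on the following order". The last four places in that order are "Failure: Disease Progression (FDP), Survival (Sur), Failure: Death During Treatment (FDDT), and Not Evaluable". Neither document says when Survival is to be assigned.

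The same SAP section analyses OS and EFS by Kaplan-Meier and defines MDS objective response as CR, PR, marrow CR, cytogenetic response or stable disease. SAP VI.J.2 reserves Not Evaluable for patients without any response assessment after baseline.

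**The concern.** A list of endpoints has been turned into a response code. Being alive is true of every patient at every visit, so it does not describe the disease. The row that the code seems to come from is mostly about deaths and failures, so it gives no guidance in the other direction either. Because the code ranks above death during treatment and above Not Evaluable, it can displace both. Response documentation serves the primary objective on adequacy of dose and duration, and the planned minimum is three patients per cohort or sub-cohort, so a single wrong label is noticeable.

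**Working it through.** The plan states no figure on this point, so there is none to reproduce. The check applies the SAP's own order.

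**Ranks, from SAP VIII.A (MDS):** CR 1, PR 2, CRm 3, CyR 4, SD 5, Rel 6, DP 7, FDP 8, Sur 9, FDDT 10, NE 11.

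**Rule:** best response = the category with the lowest rank among those recorded for the patient.

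| Categories recorded (illustrative) | Best response, SAP order | With Sur deleted from the order and from the record |
|---|---|---|
| FDDT | FDDT | FDDT |
| NE, FDDT | FDDT | FDDT |
| Sur, FDDT | **Sur** | FDDT |
| Sur only | **Sur** | NE, if the Not Evaluable rule is extended |
| DP, Sur, FDDT | DP | DP |
| SD, Sur, FDDT | SD | SD |

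The label goes wrong only when Sur has been recorded and nothing in ranks 1 to 8 has. A treatment death recorded on its own is still reported as FDDT.

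**Could an assessed patient have nothing in ranks 1 to 8?** Table 15 requires more than 8 weeks (8 × 7 = 56 days) without progression for stable disease. The first post-baseline marrow in the schedules shown in Protocol 16.1 comes earlier:

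- Cohort 1: end of Cycle 2, 14 + 14 = Day 28.
- Cohorts 3 and 3χ: Cycle 2 Day 21, 21 + 21 = Day 42.
- Cohorts 4 and 4χ: Cycle 1 Day 28.

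An MDS patient with neither response nor progression at that marrow fits no Table 15 response category yet. That an investigator would then choose Survival is an inference; the documents do not say so.

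**What else uses Sur?**

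- Objective response rate: Sur is not in the responder set. Patients labelled NE remain in the Efficacy Population as SAP VI.J.2 words it, so moving a patient from Sur to NE changes neither numerator nor denominator.
- OS: the event is death. Sur is not used.
- EFS: the events are resistance, relapse, progression or death. Sur is not used.

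**The case against.** The strongest reply is that the harm depends on data nobody can see here. Survival must be entered at an assessment, with nothing better on record, before a treatment death. Neither the eCRF nor its completion instructions are available. That stands, and it is why no count can be given.

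It is also fair that best response always masks later events: stable disease followed by death on treatment gives stable disease, and progression followed by death gives progression. But those labels report a disease finding under a stated criterion. Survival reports none.

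Some stronger readings are tempting, and the documents do not support them:

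- A reader might infer that the plan conceals treatment deaths. It does not. Deaths are evaluated under the primary safety endpoint and collected on a separate form, death is an event for both OS and EFS, and all response data are listed.
- A reader might infer that the category makes efficacy look better. It ranks ninth of eleven, below progression, and lies outside objective response.
- A reader might infer that a per-cohort best-response table is distorted. SAP VIII.A promises a per-cohort summary of the visit response; it does not expressly describe such a table for best response. One patient in a cohort of three would be 1/3, or 33 percentage points, but this is only an illustration, since MDS numbers per cohort are not given.
- The absence of a Survival category from the AML list is not in itself a fault. The two diseases use different criteria by design.
- Table 15 is not wrong as a list of endpoints. The fault lies in the SAP's use of it.

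**Conclusion.** The point holds in a limited form. The SAP programs a response category that has no assignment criterion and ranks it above death during treatment and Not Evaluable. Where it is recorded for an MDS patient with none of the eight higher categories, a death that Table 15 classes as Failure is derived as best response Survival, and a patient with no disease information can escape Not Evaluable.

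The size is confined to MDS response labels, with no change to objective response rate, OS, EFS or the safety reporting of deaths. The conclusion assumes that Survival can be entered as a response on the eCRF, which its place in a programmed order suggests but does not prove.

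**What to change.** In SAP VIII.A, delete Survival (Sur) from the MDS best-response order, so that FDDT stands for a treatment death with no better category. In SAP VI.J.2, extend Not Evaluable to patients whose post-baseline assessments meet no Table 15 response category. Query any Survival entry already on the eCRF rather than overwrite it, because the response is the investigator's determination. Report survival only through the Kaplan-Meier analyses of OS and EFS.

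Defining Survival with a visit-level criterion would also close the gap, but it would add nothing that OS and EFS do not already report.

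The cost is a small edit to the SAP and the response program, possibly some data queries, and perhaps a few more MDS patients shown as failure or Not Evaluable. The SAP allows changes until database lock.
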